6.5 Enrollment, Baseline, and Randomization

6.5.1 Enrollment

The enrollment/baseline visit will take place at the participants' homes or an office where comfort and confidentiality is assured. There is no clinic visit associated with this study. The purpose of this visit is to have in-person time to collect baseline data, explain all forms, go over the schedule of visits and intervention, and give the participant the initial compensation. No physical exams or medical assessments will be conducted as part of the screening or enrollment process.

6.5.2 Baseline Assessments

Once informed consent is given and it is confirmed that the participant meets all inclusion and exclusion criteria, baseline data will be collected. These include: Baseline Health Status and Demographic Information.

Stools will be collected multiple times throughout the study. Research staff will be trained on how to properly transport stool and how to instruct participants on collecting stool.

During the initial visit, participants will also be given all materials to collect stools, the diary, and study materials as well as the initial compensation. The participant will commence the 30-day run-in period. During this 30-day run-in period, the participant will refrain from antibiotics and probiotics (a "What Not to Eat list will be provided) and provide two baseline stool samples--one pre run-in, and one post run-in (prior to starting the yogurt and antibiotics).

Additionally, the research staff will phone the participant two times during the run-in period to collect 24-hour diet recall data. The instrument, the Automated Self-Administered 24-Hour (ASA24®) Dietary Assessment Tool, will be administered by the research staff and recorded for one weekday and one weekend day (<https://epi.grants.cancer.gov/asa24/>).

Following the run-in period and prior to the yogurt start day (day 1), research staff will contact the participant in order to complete the Post Run-in Health Status form and repeat the Inclusion/Exclusion form to ensure that the participants are still eligible. Participants who start an exclusionary medication or experience an onset of an exclusionary, nontransient health condition from the time of enrollment will be withdrawn from the study.

Should the participant take any antibiotics during this 30-day run-in period, they will start another 30-day run-in cycle after the antibiotics are completed. The initiation of the yogurt and antibiotic interventions (day 1) will be delayed until this additional run-in cycle is complete. Participants who take any non-study probiotics during this 30-day run-in period will document any use on the Post Run-In Health Status form. Participants who need to delay their day 1 (initiation of the yogurt and antibiotic intervention), e.g. to complete a full 30-day run-in or due to transient conditions, can be held for a future cohort for up to 90 days from the day the informed consent was signed, without the need to re-consent. After 90 days, the participant will be re-consented prior to starting the interventions.

Participants who are still eligible based on the completion of the Post Run-in Health Status and post run-in Inclusion/Exclusion forms will then be randomized to receive the BB-12 yogurt or control yogurt for days 1 through 14 to be taken once a day. In addition, they will also receive measuring cups that denote a level of 4 ounces. The amount of BB-12 supplemented yogurt drink to be supplied will be 4 ounces per day, which is slightly more than 100 grams/day.

6.5.3 Randomization

The group allocation ratio is 2:1, 40 BB-12 to 20 control volunteers. The randomization scheme will be generated by the study statistician, [name], using permuted blocks in random order: 4 blocks with the block size of 9 and 4 blocks with the block size of 6. It will be impossible for research personnel involved with participants to adjust randomization or discern what drinks participants were receiving, ensuring true allocation concealment. Participants who receive the control product will receive all identical interventions (i.e. stool collection, follow-up, etc.) that the BB-12 group receives.

Randomization will be completed after the participant consents to the study and completes the baseline assessment and run-in. The yogurt or antibiotic interventions may only be initiated after randomization.

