5.2.1.2 Formulation, Packaging, and Labeling

The probiotic-supplemented yogurt is composed of the investigational agent, *Bifidobacterium animalis* subsp. *lactis* (*B. lactis*) strain BB-12 (BB-12), and also contains the yogurt starter culture, YF-L702 (a mixed culture of *Streptococcus thermophilus* and *Lactobacillus delbrueckii* subsp. *bulgaricus*).

The Chr. Hansen Culture Collection (CHHC) numbers of the exact strains used in the manufacture of the yogurt blend YF-L702 are *Streptococcus thermophilus* ST5389, *Streptococcus thermophilus* ST5086, *Streptococcus thermophilus* ST4460, *Lactobacillus delbrueckii* subsp. *bulgaricus* LB4351, and *Lactobacillus delbrueckii* subsp. *bulgaricus* LB2164.

Once manufactured, the probiotic-supplemented yogurt-drink will be packaged in pint-size plastic containers, which will yield 4 servings of the 4-ounce daily dosage. Four containers of the yogurt drink with their randomly assigned bin number will be provided to the participants after enrollment and the 4-week run-in period, prior to day 1, along with the plastic cups and markings that denote levels of 2, 4, 6, and 8 ounces. The daily dose is one serving of 4-ounces of yogurt each day. This will deliver no less than 10^{10} CFU per day of BB-12.

Each plastic container will bear the label "Caution: New Drug-Limited by Federal (or United States) law to investigational use" in addition to its manufactured date and time.

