6.6 Blinding

Each participant will be randomly allocated in a 2:1 ratio to either BB-12-supplemented yogurt or an identical yogurt without the added BB-12 probiotic. Both contain the starter culture YF-L702 (a mixed culture of *Streptococcus thermophilus* and *Lactobacillus delbrueckii* subsp. *bulgaricus*). The yogurts are similar in taste and will have identical nutritional value, such as the same amount of calcium, protein, calories, etc. The yogurts are packed in identical packaging with six different bin numbers. The participants, PIs, research staff are all blinded to the treatment allocation.

The study statistician, [name], will generate three group-labels (e.g. A, B, C) where two groups are the same, e.g. A=C: BB-12 group, B: control group. [name] will be blinded to which two are the two treatment groups and which one is the control group. These groups will be considered as three arms before unblinding.

PSU will send yogurt in six bins with distinct numbers, two of which will be control yogurt and four will be the BB-12 yogurt. Only the researchers at Maryland will know which bin numbers correspond to 'group 1' and which correspond to 'group 2', but will not know which is the active or control. PSU and Maryland have no contact with participants and will not release this information to the study team until the analyses are completed and databases are locked.

All study personnel at Georgetown and [name] will remain blinded throughout the study until the databases are locked. In the unfortunate event that a participant experiences a serious adverse event or emergency that requires unmasking the treatment groups, [name], a member of the Department of Family Medicine who is not affiliated with the study, will discuss the assignment and follow-up with the participant and their treating physician. [name] has done this for our previous clinical trials.

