6.7.2 Telephone Follow Up Script

In general, the Day 7, 14 and 30 (± 2 days) follow up will be administered over the phone, but may be completed in person. These phone visits are when the primary data will be collected. It is imperative that all visits be completed on a timely and regular fashion.

- 1) *Drink Bin Number:* Make sure the participant has the correct drink bin number as you are completing the Follow-Up Form.
 - a) Ask the participant the number on the drink bottles and this should be confirmed with the randomization form.
 - b) If this number is not consistent, the participant should be alerted not consume any more drinks until further notice and the project coordinator should be immediately alerted after completing this week's Follow-Up Form.
- 2) *Daily Assessment Diary:* Ask the participant to collect the Daily Assessment Diary for the phone conversation. A lot of the information that will be collected on the Follow-Up Form has been collected by the participant on their Daily Assessment Diary. If they have not been using the Daily Assessment Diary, please positively stress the importance of the Daily Assessment Diary.
- 3) Explain to participant that we are supposed to fill out this Follow-Up Form today and it should take about 5 minutes.
- 4) Administer Follow-Up Form.
 - When entering sick days, missing school or work, etc., this should be generally whole integers. However, it is possible that a participant missed only 2 hours to go to the doctor. All numbers under 4 hours should be counted at 0.5 days, and all those above rounded up to next integer.
 - The participant needs to decide if any activities were missed due to an illness. This is for all illnesses, even those that we are not collecting data about.
 - For some questions the RA may say, "Did you visit a doctor?" A doctor is defined as any medical personnel in this study. Therefore, the participant may say, "Never, but s/he saw a nurse practitioner." Please count this the same as seeing the doctor.
 - *Compliance:* Please let the participant know that we would like them to consume the interventions, diaries, and sample collections as per the schedule, but regardless, we appreciate their participation.
 - *Adverse Events:* If the participant believes any AE occurred, it is imperative that the RA immediately fill out an AE Form, and if there are any SAE, alert the PI and project coordinator immediately.
 - Confirm the date and time for the next visit or call.

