9.2 Sample Size and Randomization

Sample size calculations were informed by data from Hoverstad et al.,(120, 121) which compared changes in the mean SCFA levels between baseline fecal samples and fecal samples collected after six days administration of various antibiotics or placebo in healthy volunteers. In these studies, a mean reduction in acetate levels occurred from 45 ± 16 umol/g at baseline to 24 ± 18 umol/g after antibiotic treatment (46% reduction in acetate). Reductions in acetate after antibiotic treatment ranged from 5% to 79% with ampicillin, a similar antibiotic to amoxicillin.(120, 121) We can infer similar decreases in acetate in our proposed study. Using a conservative estimate of a 42% decrease in acetate in the control/antibiotic treated group and no greater than a 15% decrease in the BB-12 treated group, and an allocation ratio of 2:1 (BB-12 to control volunteers); a total sample size of 60 participants is necessary to have 80% power to detect a significant difference in mean acetate levels as a measure of gut microbiota production of SCFA between a control and BB-12-treated group.

With a sample size of 40 subjects in the active arm and 20 subjects in the control arm and attrition rate of 5% at day six and 20% at day 30, we would have power of 82% to detect a moderate effect size of Cohen's $d = 0.63$ (assuming the intra-correlation correlation coefficient is 0.3). The α level of 0.05 will be used for the analysis. Since the effect size of previous study (reduction in acetate levels) is Cohen's $d = 1.23$, we should have ample power to detect the treatment effect. (The power calculation is based on the R software and packages simr, sjstats, and pwr).

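### Reused bin numbers visible to site staff, together with a fully printed block plan, mean that section 6.5.3 cannot claim the drinks are impossible to discern; how much leaks depends on list-building rules the protocol does not state

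*Combined protocol and SAP*

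**What the plan says.** Protocol section 6.5.3 gives the ratio, "The group allocation ratio is 2:1, 40 BB-12 to 20 control volunteers", and the complete block plan, "using permuted blocks in random order: 4 blocks with the block size of 9 and 4 blocks with the block size of 6". Only the order of the blocks is left open. The same section states: "It will be impossible for research personnel involved with participants to adjust randomization or discern what drinks participants were receiving".

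Section 6.6 describes the coding: "PSU will send yogurt in six bins with distinct numbers, two of which will be control yogurt and four will be the BB-12 yogurt". It also describes three group labels (A, B, C), two of them BB-12 and one control, to be handled as three arms until unblinding. The same section then speaks of bins belonging to a group 1 and a group 2.

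The bin number reaches both the participant and the staff. Section 5.2.1.2: "Four containers of the yogurt drink with their randomly assigned bin number will be provided to the participants after enrollment". Section 6.7.2, for the follow-up calls: "Ask the participant the number on the drink bottles and this should be confirmed with the randomization form". Section 9.2.1 has a web-based system issue assignments automatically.

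The protocol does not say whether the blocks balance two arms or three labels, how a bin is picked within an arm or label, or whether a bin number keeps its meaning from one yogurt shipment to the next.

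**The concern.** Six codes shared by 60 people give about 10 people per code, so working out a code unblinds a whole group and not one person. A reader of the protocol knows that exactly two of the six codes are control. If the blocks are built on arms, that reader also knows that every block of 6 holds exactly 2 controls and every block of 9 exactly 3. There are only 15 candidate control pairs, and a wrong pair will tend to break those block totals as the log grows.

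At this single site the staff who see bin numbers also collect adverse events and follow-up data (sections 6.7.2 and 10.1). The investigator's view of relatedness decides whether some events are followed past day 14 (section 7.7), and the investigator discusses withdrawals for adverse events (section 8). Participants whose start is delayed "can be held for a future cohort for up to 90 days from the day the informed consent was signed". Knowledge of the arm could colour those judgements. Late in a block it could also help someone predict the next assignment.

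**Working it through.** **1. The block plan reproduces the stated sizes.**
- Total: 4×9 + 4×6 = 60.
- Control: 4×3 + 4×2 = 20. BB-12: 4×6 + 4×4 = 40.
- Possible block orders: C(8,4) = 70.

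**2. What the blocks can balance.** 9/6 = 1.5, so a block of 9 cannot use six bins equally. The blocks must balance arms or labels. Both 9 and 6 divide by 3, so either is possible.

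**3. Scoring a candidate control pair.** There are C(6,2) = 15 pairs, so chance is 1/15 = 7%. For each pair, mark every participant in the ordered log as in or out of that pair.
- A completed block of size s with k = s/3 controls contributes 1/C(s,k) if its count is exactly k, and 0 otherwise.
- A block under way, with c controls in its first m places, contributes C(s−m, k−c)/C(s,k).
- Average over the unknown block order and multiply by (1/2)^c × (1/4)^(n−c), where c is now the total count in the pair among n participants. This is the bin factor when bins are drawn at random within arm.
- Normalise over the 15 pairs to get the posterior.

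**4. Blocks built on two arms.** Percentage of simulated trials in which the best guess is the true control pair, over repeated runs:

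| Bin rule within arm | n = 30 | n = 45 | n = 60 |
|---|---|---|---|
| Drawn at random | about 80–83 | 95–96 | over 99 |
| Each bin used 10 times | about 74–76 | 92–95 | 96–97 |

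Certainty arrives later than a good guess. With random draws, only the true pair remains possible in 38% of trials at n = 30, 69% at n = 40 and 98% at n = 60.

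Two other rules behave differently. An observer who scores as in step 3, not knowing the rule, is left with about 11 of 15 pairs at n = 60 if bins are issued in shuffled balanced sets, and about 10 of 15 if they follow a fixed rotation. An observer who knows the rule picks correctly in 53/66/80% of trials (shuffled sets) and 98/99/100% (rotation) at n = 30/45/60.

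**5. Blocks built on A/B/C, two bins per label.** The six bins split into three pairs in 6!/(2!³×3!) = 720/48 = 15 ways. The true split is recovered in about 93% of trials at n = 30 and 99% at n = 45. The three labels are interchangeable in the sequence, so about 3 candidate control pairs remain at n = 60 and the posterior for the true one is about 0.33. Once the split is known, one unmasked control participant identifies the control pair and so all 20 controls.

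**6. Prediction if the arms were decoded.** On average 5.2 of 60 assignments are certain in advance, and 43.8 of 60 can be guessed correctly, against 40 by always guessing BB-12.

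**The case against.** The strongest objection is that section 6.6 favours the three-label reading. The labels are to be handled as three arms, the list-maker appears not to know which label is control, and equal A/B/C blocks of 6 or 9 give 2:1 automatically. On that reading the sequence alone can never single out control. This stands, and it rules out a reading that a reader might be tempted to adopt: that the printed plan and the log are enough to unblind everyone, so that concealment fails. The documents do not support that, because they do not fix the level of blocking or the bin rule.

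Other parts also stand. The calculation needs bin codes to keep their meaning while product with a one-month shelf life is replaced (sections 5.2.4.2 and 5.2.4.5), someone who holds the numbers in randomization order, and someone willing to do the inference. Section 6.7.2 shows staff checking one participant's bin at a time. Certainty comes mostly late in accrual.

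Nor can a reader infer that the primary result would be biased. Fecal acetate is measured by LC-MS/MS (sections 3.1 and 6.2.1.3), participants complete the diaries (section 10.2.3), and randomization follows the post-run-in eligibility check (section 6.5.2). Holding a participant for a later cohort is described for completing the run-in or for transient conditions.

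The objection does not rescue the absolute claim. Under the three-label reading, knowledge of control still rises from 1 in 15 to about 1 in 3, and the bin pairings are exposed.

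**Conclusion.** The concern holds in conditional form. Six reused, visible codes and a fully printed block plan mean that the protocol cannot promise that discerning the drinks is impossible.

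- **Arm-level blocks with random or equal bin use:** the control pair can be picked in about 75 to 83% of trials at 30 participants and 96 to over 99% at 60. This assumes stable bin codes and an observer with the ordered log.
- **Arm-level blocks with other bin rules:** little leaks unless the rule is known.
- **A/B/C blocks:** control remains about a 1-in-3 guess, with all 20 controls exposed by a single unmasked control participant.

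The exposure is mainly in adverse-event relatedness, follow-up and withdrawal judgements, and in late assignments. The documents do not show that blinding or concealment has failed, or that the acetate comparison is compromised. The change is still worth making, because it is cheap and removes the leak under either reading.

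**What to change.** 1. In 6.5.3, build the list on the six bin numbers, each appearing equally often in every block. For example, use four blocks of 6 (each bin once) and three blocks of 12 (each bin twice), in random order. Check: 4×6 + 3×12 = 60; controls 4×2 + 3×4 = 20; each bin used 4×1 + 3×2 = 10 times; 2:1 in every block. The bins are then interchangeable, and the sequence leaves the control pair at 1/15.
2. Move the number and sizes of blocks from the protocol to a document held by the statistician.
3. Delete the statement that discerning the drinks is impossible.
4. Reconcile the two-group and three-label descriptions in 6.6. As written, those who know which bins form group 1 and group 2 are said not to know which is active, yet a split of four bins against two would tell them.

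The cost is a new list in the existing web-based system and a short protocol edit, with no extra product or participants. The last bin numbers in a block may be guessable, but they would not point to an arm. Participant-level kit codes would also remove the shared codes.

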6.6 Blinding

Each participant will be randomly allocated in a 2:1 ratio to either BB-12-supplemented yogurt or an identical yogurt without the added BB-12 probiotic. Both contain the starter culture YF-L702 (a mixed culture of *Streptococcus thermophilus* and *Lactobacillus delbrueckii* subsp. *bulgaricus*). The yogurts are similar in taste and will have identical nutritional value, such as the same amount of calcium, protein, calories, etc. The yogurts are packed in identical packaging with six different bin numbers. The participants, PIs, research staff are all blinded to the treatment allocation.

The study statistician, [name], will generate three group-labels (e.g. A, B, C) where two groups are the same, e.g. A=C: BB-12 group, B: control group. [name] will be blinded to which two are the two treatment groups and which one is the control group. These groups will be considered as three arms before unblinding.

PSU will send yogurt in six bins with distinct numbers, two of which will be control yogurt and four will be the BB-12 yogurt. Only the researchers at Maryland will know which bin numbers correspond to 'group 1' and which correspond to 'group 2', but will not know which is the active or control. PSU and Maryland have no contact with participants and will not release this information to the study team until the analyses are completed and databases are locked.

All study personnel at Georgetown and [name] will remain blinded throughout the study until the databases are locked. In the unfortunate event that a participant experiences a serious adverse event or emergency that requires unmasking the treatment groups, [name], a member of the Department of Family Medicine who is not affiliated with the study, will discuss the assignment and follow-up with the participant and their treating physician. [name] has done this for our previous clinical trials.

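### Section 6.6 says the Maryland holders of the two-group bin map cannot tell which group is active, but the 4:2 bin split stated in the same paragraph tells them

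*Combined protocol and SAP*

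**What the plan says.** Section 6.6 describes two masking devices, one after the other.

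- **Three labels.** The statistician generates three group labels, two of which are the same product. A person whose name is removed from the public text "will be blinded to which two are the two treatment groups and which one is the control group". Of the labels, the section says: "These groups will be considered as three arms before unblinding".
- **Two-group bin map.** Penn State sends six numbered bins, "two of which will be control yogurt and four will be the BB-12 yogurt". The next sentence begins "Only the researchers at Maryland will know which bin numbers correspond to" and goes on to name group 1 and group 2. It adds that the Maryland researchers will know this "but will not know which is the active or control".

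The section also says: "The participants, PIs, research staff are all blinded to the treatment allocation". Penn State and Maryland are described as not dealing with participants. They "will not release this information to the study team until the analyses are completed and databases are locked". The following paragraph says that Georgetown personnel and a named person "will remain blinded throughout the study until the databases are locked".

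Elsewhere, the Précis (Interventions and Duration) uses Group 1 for the BB-12 arm (n=40) and Group 2 for the control arm (n=20). Section 6.5.3 gives the 2:1 allocation in four blocks of 9 and four blocks of 6.

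**The concern.** A two-group code hides the product only if the groups cannot be told apart by size. Here they are unequal in bins (4 and 2) and in participants (40 and 20), and the protocol states both splits. Anyone who holds the complete map can read off the control group.

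The three-label scheme appears designed to prevent this, because it turns one arm of 40 and one of 20 into three of equal size. The two-group map removes that protection for its holders, and the section does not say how the two schemes fit together. If group 1 and group 2 in section 6.6 mean what they mean in the Précis, the labels name the product outright.

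At stake is first whether the blinding statement is accurate: a report could not truthfully say that the map holders were blinded. Second, Maryland is not a remote packaging site. The study-team page lists a laboratory principal investigator, a laboratory co-investigator and the biostatistician there, and section 6.2.1.2 sends the stool to the Institute for Genomic Sciences. If the map holders include people who run the assays or the analysis, they would do so knowing the arms. The documents leave that open.

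**Working it through.** **Inputs.** Six bins, four BB-12 and two control (6.6). A map of bins to two groups held at Maryland (6.6). Allocation 40:20 in four blocks of 9 and four blocks of 6 (6.5.3). Group 1 = BB-12, n=40, and Group 2 = control, n=20 (Précis).

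**Step 1. Check that the plan's own figures agree.**
- Bins: 4/2 = 2. Participants: 40/20 = 2.
- Blocks: 4×9 + 4×6 = 60 in total. BB-12: 4×6 + 4×4 = 40. Control: 4×3 + 4×2 = 20.

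The 4:2 bin split and the 2:1 allocation are consistent.

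**Step 2. No map.** The number of ways to choose the two control bins from six is C(6,2) = 6!/(2!×4!) = 15.

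**Step 3. The two-group map in 6.6.** The map divides the bins into a set of four and a set of two. Only one assignment has exactly two control bins, all in one group: the two-bin group is control. So 1 of 15 remains. A holder who knew neither the 4:2 split nor the 2:1 ratio would face 2 possibilities, but the protocol states both figures. Participant counts lead to the same answer, since the group of 40 is BB-12.

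**Step 4. An A/B/C map instead.** Assume two bins per label, which the text does not state but which six bins and three labels allow. The control pair is then A, B or C, so 3 assignments remain and a guess is right 1 time in 3. Each label has 4×3 + 4×2 = 20 participants, so size no longer gives control away.

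**Step 5. Both maps together.** 1 assignment remains. Adding the two-group map cancels what the three labels protect.

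| Information held | Assignments left |
|---|---|
| No map | 15 |
| A/B/C map, two bins per label | 3 |
| Two-group map with the 4:2 split | 1 |
| Both maps | 1 |

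**The case against.** The strongest reply is that the blinding that protects the trial is intact. Maryland does not deal with participants, Georgetown staff stay blinded, a named person is kept from knowing which label is control, and the primary outcome is an instrument reading. All of this stands, and it limits the consequence. It does not make the sentence about the map holders true.

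A second reply is that the wording is loose and the two groups are shorthand for the three labels. Six bins would fit three labels of two. But section 6.6 does not say so, and the Précis uses the same two terms for the two arms.

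A reader might infer three stronger things that the documents do not support.
- *That the statistician or the Maryland principal investigator is unblinded.* The map holders are described only as researchers at Maryland, and names are removed from the public text. If the Maryland principal investigator does hold the map, the sentence that the PIs are blinded fails too, but that is conditional.
- *That the two release statements contradict each other and allow the model to be chosen with the arms known.* They have different subjects: one governs when Penn State and Maryland release information, the other how long Georgetown and a named person stay blinded. The first is stricter, and following it satisfies both. The open model choices in section 9.7 are a separate matter, whoever holds the bin map.
- *That the acetate result is biased.* Nothing in the documents shows this or allows its size to be estimated.

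**Conclusion.** Wrong as written, of minor to moderate weight. The claim that the map holders cannot tell active from control is incompatible with the split stated beside it: 1 of 15 assignments remains, where an A/B/C map would leave 3. The count rests on two assumptions: the Maryland map covers all six bins, and its holders know the 4:2 or 2:1 split. The figure of 3 also assumes two bins per label.

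Confidence is high in the counting point. Its practical effect depends on who holds the map, which the documents do not say. A breach of blinding for participants or Georgetown staff is not shown, and any bias in the acetate outcome is probably small and not quantifiable from the documents.

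**What to change.** In section 6.6:

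1. Replace the two-group map with a map of the six bins to labels A, B and C, two same-product bins per label. Generate the randomization list in those labels: 3 of each per block of 9 and 2 of each per block of 6. That gives 20 per label and keeps 40:20.
2. Have Penn State hold the label-to-product key, and state how it is reached for the emergency unmasking that the section already describes.
3. State by role who holds each list, and whether the statistician and the Maryland principal investigator are among them.
4. Word the release point identically in both paragraphs, using the stricter one already there: after both database lock and completion of the analyses.
5. Keep *B. lactis* PCR results (sections 5.2.5 and 5.4) and 16S results (section 6.2.1.4) by label from the acetate analysts until that point.

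If the two-group map is kept, delete the claim that its holders are blinded.

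The cost is a few sentences and a new label file, with no new staff, samples or assays. The masking would be better but not perfect: PCR or 16S results seen by label, or a real BB-12 effect on acetate seen by label, could still reveal the control label. The 1-in-3 figure is therefore a best case.
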